6.1. Statistical Definitions and Algorithms

6.1.1. Baseline

The last observation recorded before the first administration of IP will be used as the baseline observation for all calculations of change from baseline.

6.1.2. Adjustments for Covariates

The adjustments for covariates will be performed for analyses of data from Part 2 and for analyses of the Combined Population.

An analysis of covariance (ANCOVA) with the treatment as covariate will be used. When the analysis is based on a continuous endpoint, the baseline value of the endpoint will be included as a covariate. Endpoint analyses will also be adjusted for the following, *a priori* specified covariates: diabetes (dichotomous), age (continuous), body mass index (continuous), baseline sPLA2 activity (continuous). Each of these variables is known to be associated with outcomes in patients with severe COVID-19 infection. Each of these variables will be assessed at baseline, prior to randomization. Additional covariates will be considered for inclusion in the adjusted models if there is significant imbalance between the two arms of the trial.

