8.1. Primary Efficacy Analysis

The primary efficacy endpoint is the proportion of participants alive and free of respiratory failure at Day 28.

The proportion of respiratory failure-free surviving participants in each Part 2 treatment group at Day 28 will be analyzed using logistic regression with treatment as a factor and age, diabetes, body mass index, and baseline sPLA2 activity included as covariates. Dummy/reference coding will be used in all logistic regression implementations. The risk difference between varespladib and placebo along with the 95% CI and p-value will be presented. Note that logistic regression typically involves calculation and testing of odds ratios, however, this analysis will focus on presenting and testing the risk difference via the delta method ([Ge et al, 2011](#)).

The ITT, PP and Combined populations will be used to analyze the primary efficacy endpoint. The ITT population will be the primary population for the efficacy analyses.

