8.1.1. Sensitivity Analyses of the Primary and Key Secondary Efficacy Endpoints

Two types of sensitivity analyses will be conducted for the primary efficacy endpoint and key secondary efficacy endpoints using the ITT population. The following sensitivity analysis will be conducted in Part 2 subjects only.

One sensitivity analysis will be to examine the effect of covariate selection. This work will include estimating (1) the effect of treatment on the outcome adjusted for only the *a priori* specified model covariates (see section 6.2.1), and (2) and if significant imbalance is observed in other important covariates, then adjustment for the *a priori* specified covariates as well as other variables that are imbalanced between the treatment arms.

A second sensitivity analysis will be stratified estimates of the effect of treatment. The following strata will be examined: 1) high or low sPLA2 activity, with high defined as the median sPLA2 value or greater, 2) male or female gender, 3) high or low SpO2 at baseline dichotomized based on median value; 4) baseline WHO ordinal scale score dichotomized based on the median value; and 5) use of remdesivir or dexamethasone at baseline. Stratified estimates for a given variable will not be conducted if the number of patients within a stratum are insufficient to support the analysis.

Sensitivity analyses are exploratory and will be interpreted as evidence to inform additional research. The above listed sensitivity analyses will be applied to the primary efficacy endpoint and the following key secondary endpoints: days of oxygen support through day 28, ICU days through day 28, 9-point WHO clinical status scale, and mortality through Day 60.

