8.2.1. World Health Organization (WHO) 9-point Ordinal Scale

The investigators will assess participants' clinical status using the WHO 9-point ordinal scale:

| Patient State | Descriptor | Score |
|------------------------------|--|-------|
| Uninfected | No clinical or virological evidence of infection | 0 |
| Ambulatory | No limitations on activities | 1 |
| | Limitation on activities | 2 |
| Hospitalized; mild disease | No oxygen therapy | 3 |
| | Oxygen by mask or nasal prongs | 4 |
| Hospitalized; severe disease | Noninvasive ventilation or high-flow oxygen | 5 |
| | Intubation and mechanical ventilation | 6 |
| | Ventilation plus additional organ support (pressors, renal replacement therapy (RRT), extracorporeal membrane oxygenation (ECMO) | 7 |
| Dead | Death | 8 |

Descriptive summaries of observed values and changes from baseline in the WHO 9-point scale will be presented for each scheduled visit within treatment group. Distribution of outcomes on the WHO ordinal scale will also be described via plots in supplemental analyses.

Mean change from baseline in the WHO 9-point scale for each assessment will be analyzed using ANCOVA at each scheduled post-baseline visit. The model will include treatment, age, diabetes, body mass index, and baseline value as covariates. The least squares (LS) mean change from baseline will be presented along with the associated 95% CI within each treatment group. In comparing treatments, LS mean differences in change from baseline between treatments will be presented along with associated 95% CIs and p-values. Participants that die will have a score of 8 assigned to all scheduled visits on and after the date of death.

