8.2.12. Days of Oxygen Support

The number of days of oxygen support from randomization through Day 28 will be summarized descriptively and analyzed using ANCOVA. The LS means will be presented along with the associated 95% CI within each treatment group. In comparing treatments, LS mean differences between treatments will be presented along with associated 95% CIs and p-values. In order to assign the worst total score for death, participants that die will have all days from randomization through day 28 treated as if they were on oxygen support.

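### The day-count ANCOVAs do not adjust a priori for respiratory status at entry; baseline WHO score (3 v 4) should be added to them

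*SAP*

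**What the plan says.** SAP 6.1.2 fixes four covariates for the endpoint analyses of Part 2 and the Combined Population: "diabetes (dichotomous), age (continuous), body mass index (continuous), baseline sPLA2 activity (continuous"). It adds one rule: "When the analysis is based on a continuous endpoint, the baseline value of the endpoint will be included as a covariate". It ends with a conditional clause: "Additional covariates will be considered for inclusion in the adjusted models if there is significant imbalance between the two arms of the trial".

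The day-count sections (SAP 8.2.7 to 8.2.10 and 8.2.12) name the method without listing covariates, for example "The number of days of oxygen support from randomization through Day 28 will be summarized descriptively and analyzed using ANCOVA", so 6.1.2 governs them. Each scores a death as the worst possible total. Protocol 13.1.4.3 puts only treatment in these models and leaves further covariates to the SAP.

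The WHO-scale model does carry its own baseline (SAP 8.2.1: "The model will include treatment, age, diabetes, body mass index, and baseline value as covariates"). SAP 8.1.1 plans a covariate-selection sensitivity analysis and stratified estimates, one of them by "baseline WHO ordinal scale score dichotomized based on the median value" and another by baseline SpO2. These cover the primary endpoint, oxygen days, ICU days, the WHO scale and mortality.

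The WHO score is assessed at screening in every participant (Protocol 10.2.1). Randomisation is blocked by centre (Protocol 9.7) with no stratification variables (SAP 3.2).

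**The concern.** A count of days after randomisation has no value before randomisation, so the baseline rule in 6.1.2 adds nothing to these models. The natural substitute is whether the participant was already on oxygen at entry, that is, WHO 3 v 4. The exclusion criteria remove high-flow oxygen above the stated limits, non-invasive ventilation and intubation, but not low-flow oxygen, so 3 v 4 is the contrast that remains. The SAP treats this variable as important enough to stratify on in 8.1.1, but not as an a priori term where it would sharpen the estimate.

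Two things are at stake: precision in a comparison of 36 per arm, and the accuracy of a given result when the arms happen to differ in entry oxygen use. The imbalance clause is the only route by which hospital, ventilator-free and organ failure-free days could be adjusted. It has no threshold and no variable list, and it commits only to considering extra covariates.

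**Working it through.** The plan gives no power, effect size, SD or event rate, so there is no figure of its own to reproduce.

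**Inputs from the documents.** Part 2 has 72 participants randomised 1:1, so 36 per arm. The planned models contain treatment and four covariates. Deaths score 28 days of oxygen, ICU or hospital.

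**Assumed inputs.** Share q at WHO 4: 30% to 80% for imbalance, 60% for variance. Difference d in oxygen days between WHO 4 and WHO 3 among survivors, after the four covariates: 3 to 6. Residual SD s among survivors: 5 to 6. Mean for WHO 3 survivors: 4 to 6 days. Deaths: 10% in both WHO groups, or 5% v 15%.

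**1. Chance imbalance.** SD of the between-arm difference = sqrt(2q(1-q)/36).
- q = 0.5: sqrt(0.50/36) = 0.118. q = 0.8: sqrt(0.32/36) = 0.094.
- With two Binomial(36, q) arms, a gap of 10 points or more occurs in 30% to 41% of trials, and one of 20 points or more in 3% to 8%.
- If the trigger is read as a two-sided 5% test (the SAP does not say), then at q = 0.5 the gap must reach about 1.96 x 0.118 = 23 points.
- A gap of 10 points or more that misses significance occurs in 25% to 37% of trials.

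**2. Variance inflation, ignoring deaths.** Inflation = 1 + q(1-q)d²/s².
- q = 0.6: from 1 + 0.24 x 9/36 = 1.06 to 1 + 0.24 x 36/25 = 1.35.
- q = 0.9: from 1 + 0.09 x 9/36 = 1.02 to 1 + 0.09 x 36/25 = 1.13.
- q = 0.95: 1.01 to 1.07.

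**3. Variance inflation with deaths scored as 28 days (q = 0.6).** Within a WHO group with survivor mean μ and death risk m, the mean is (1-m)μ + 28m and the variance is (1-m)s² + m(1-m)(28-μ)².
- *Low end:* m = 0.10 in both groups, d = 3, s = 6, means 4 and 7. Variances: 32.4 + 0.09 x 576 = 84.2 and 32.4 + 0.09 x 441 = 72.1. Weighted: 0.4 x 84.2 + 0.6 x 72.1 = 76.9. Gap: 0.9 x 3 = 2.7. Inflation: 1 + 0.24 x 7.29/76.9 = 1.02.
- *High end:* m = 0.05 and 0.15, d = 6, s = 5, means 6 and 12. Group means: 7.1 and 14.4, gap 7.3. Variances: 23.75 + 0.0475 x 484 = 46.7 and 21.25 + 0.1275 x 256 = 53.9. Weighted: 51.0. Inflation: 1 + 0.24 x 53.3/51.0 = 1.25.
- Over the whole grid: 1.02 to 1.13 with equal death rates, and 1.08 to 1.25 with 5% v 15%. The total SD is about 8 to 9 days.

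**4. Meaning of 1.02 to 1.25.** The standard error is sqrt(1.02) = 1.01 to sqrt(1.25) = 1.12 times what it need be. With the term added, 36 per arm is worth 36 x 1.02 = 36.7 to 36 x 1.25 = 45. The extra term costs a factor of about (72-3-4)/(72-3-5) = 65/64 = 1.016 in variance, so the net gain runs from about nothing to 1.25/1.016 = 1.23.

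**5. Conditional shift.** A 10-point gap in the WHO 4 share moves an unadjusted mean difference by 0.10 x 2.7 = 0.27 to 0.10 x 7.3 = 0.73 days in these two cases. The standard error is about 8 x sqrt(2/36) = 1.9 to 9 x sqrt(2/36) = 2.1 days.

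**6. The primary model, for contrast.** At failure rates of 10%, 20% and 30% (assumed) there are about 7, 14 and 22 events in 72, or 1.4, 2.9 and 4.3 per term with the planned five terms. In 3,000-run simulations, adding both WHO score and SpO2 changed the standard error of the risk difference from 3% worse to 7% better. Non-convergence rose from at most 0.4% to as much as 3.2%, and rejection under the null from 6.1-7.2% to 7.0-8.4%.

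**The case against.** Three stronger readings are tempting, and the documents support none of them.

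*Chance imbalance goes uncorrected.* It does not. Section 6.1.2 allows extra covariates on imbalance. Section 8.1.1 adds an adjusted sensitivity analysis and estimates by baseline WHO score and SpO2. What stands is narrower. The correction is conditional and undefined, the stratified estimates may be skipped if strata are small, and 8.1.1 leaves out hospital, ventilator-free and organ failure-free days.

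*The primary model needs the same term.* SAP 8.1 specifies "logistic regression with treatment as a factor and age, diabetes, body mass index, and baseline sPLA2 activity included as covariates", and Protocol 13.1.4.2 fixes the same four. With so few events the gain is uncertain and may be negative. Adding WHO score there, or dropping body mass index to make room, would depart from the protocol for no assured benefit.

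*The results are biased.* Omitting a prognostic variable does not bias a randomised comparison on average. The loss is in precision and in conditional accuracy.

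The best remaining objection is that baseline WHO score may hardly vary. Protocol 7.2 speaks of excluding patients who already need oxygen, while 8.2.2 has no such exclusion for low-flow oxygen. Conversely, the low saturations among the severity signs could put nearly everyone on oxygen. Either would shrink the gain, as the 90% and 95% cases in step 2 show. It is also true that nothing now being reported depends on the choice. SAP 10 records one Part 2 participant and limits Part 1 to descriptive summaries and confidence intervals without tests.

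**Conclusion.** The point holds for the day-count ANCOVAs only, as an inexpensive improvement to a future Part 2 analysis. These models omit a severity measure that everyone has at baseline, and the safeguards do not reliably replace it. The variance penalty is roughly 2% to 25% (standard error 1% to 12%), given 60% at WHO 4, a 3 to 6 day difference and deaths scored as 28 days. The low end is about what the added term costs. These figures describe oxygen days. The documents give nothing from which to size the gain for ventilator-free or organ failure-free days, where WHO 3 v 4 may predict less. Every rate and SD here is an assumption.

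**What to change.** In the Part 2 SAP amendment that SAP 10 already promises (for other secondary endpoints):

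- Add baseline WHO score (3 v 4) to the 6.1.2 covariate list for the ANCOVAs of oxygen, ICU, hospital, ventilator-free and organ failure-free days. Take the last value before dosing, as 6.1.1 requires. In practice this is the screening value, because Protocol 10.2.2.1 lists the Day 1 assessment after dosing starts. State how any score above 4 is coded.
- In those models, use this fixed list in place of the imbalance trigger.
- Leave the primary model's main covariates as Protocol 13.1.4.2 has them. A WHO-adjusted version can be listed in 8.1.1 as a sensitivity analysis.
- Reconcile Protocol 7.2 with 8.2.2 on oxygen use at entry, since that decides whether the covariate varies.

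The cost is SAP wording and one degree of freedom per model, with little return if nearly all participants enter at one WHO level. Protocol 13.1.4.3 already leaves these covariates to the SAP, so the day-count change needs no protocol amendment.

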6.1.3. Multiple Comparisons

This is an exploratory pilot study that will be used to inform decisions about possible future

trials. No adjustments for multiple comparisons are planned.

6.1.4. Handling of Dropouts or Missing Data

Withdrawn participants will not be replaced. Randomized participants withdrawn from the study may not reenter. The subject number for a withdrawn subject will not be reassigned to another subject.

Missing data for reasons other than death will, when possible, be derived from contemporaneous clinical data. If other clinical data are not available or not determinative of the outcome, data will be imputed based on the last available value (last observation carried forward).

Participants in the ITT population who experience death will have their data after death assigned as the worst possible value within a specific scale or in regard to duration or proportion as defined by the particular outcome. Participants who do not experience a particular event will not be excluded from the analysis of duration or time-to-event endpoints and will have an appropriate value assigned.

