## 13. STATISTICS

### 13.1. Statistical Analysis

This section is a summary of the planned statistical analyses of the primary and secondary endpoints. The statistical analysis plan (SAP) with final planned analyses will be developed and finalized before database lock.

Descriptive statistical methods will be used to summarize the data from this study with confidence intervals calculated for the primary and secondary efficacy endpoints. Unless stated otherwise, the term “descriptive statistics” refers to the number of participants (n), mean, median, standard deviation, minimum, and maximum for continuous data; and frequencies and proportions for categorical data. All data collected during the study will be included in data listings.

Participants who die will have their data after death assigned as the worst possible value within a specific scale or with regard to duration or proportion as defined by the particular outcome. Participants who do not experience a particular event will not be excluded from the analysis of duration or time-to-event endpoints and will have an appropriate value assigned. Missing data for reasons other than death will, when possible, be derived from contemporaneous clinical data. If other clinical data are not available or not determinative of the outcome, data will be imputed based on the last available value (last observation carried forward).

Unless otherwise indicated, comparative statistics between treatment and control group will report point estimates, p-values, and 95% confidence intervals with the goal of understanding the clinical importance of observed effects.

This study is considered an exploratory study. Statistical tests will be interpreted in an exploratory sense only and will not be considered formal hypothesis tests.

All efficacy variables will be summarized descriptively. Primary and secondary efficacy endpoints will be tabulated according to the “Observed Cases” approach. Exploratory hypothesis testing will also be conducted for the majority of endpoints.

Part 2 efficacy summaries will be done by randomized treatment. Part 1 efficacy data will be listed only. Hypothesis testing will be evaluated in an exploratory manner in order to inform decisions about future trials.

All statistical analyses will be conducted with the SAS® System, version 9.3 or higher.

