- For the time till all-cause mortality Cox proportional hazards model, time to all-cause mortality or censoring will be calculated as follows
 - If mortality occurs within 60 days post-randomization; then Time to all-cause mortality or censoring = date/time of death – date/time baseline + 1.
 - If mortality occurs on or after 60 days post-randomization; then Time to all-cause mortality or censoring = 60 days.
 - If mortality does not occur, and last follow-up is prior to 60 days; then Time to all-cause mortality or censoring = date/time of last follow-up – date/time baseline + 1.
 - If mortality does not occur, and last follow-up is on or after 60 days; then Time to all-cause mortality or censoring = 60 days.
- Change from baseline = value at current time point – value at baseline.
- TEAE = any adverse event with an onset or worsening date/time after the date/time of the first administration of IP and prior to the 30 days after last dose of IP.

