8.2.2. All-Cause Mortality

All-cause mortality from randomization through Day 60 will be analyzed using a Cox-Proportional hazard model. The number of participants who experience the event and rate ratio with 95% CI will be presented. The p-value to test if the rate ratio between treatments differs from 1 will be evaluated. Kaplan-Meier methodology will be used to estimate the median time to the event and 95% CI. Time to all-cause mortality will be calculated according to [Section 6.1.7](#).

Censoring events include loss to follow-up prior to Day 60. Covariates will include those a priori specified in [Section 6.1.2](#), and Efron's method for handling tied time-to-events will be used. The p-value testing for non-zero treatment effect will be obtained from a Wald chi-square test, and

the 95% CI associated with the treatment effect will be a Wald-type CI.

Additionally, the proportion of participants who die will be analyzed using the same logistic regression and risk difference method with dummy coding as the primary endpoint (Ge et al, 2011). In general, the proportions of participants with an event on or before Day 60 will be analyzed.

8.2.3 Proportion of participants who experienced respiratory failure within the first 28 days after randomization

The proportion of participants experiencing respiratory failure from randomization through Day 28 will be analyzed using the same logistic regression and risk difference method with dummy coding as the primary endpoint. Respiratory failure is defined as defined by requiring HFNC >20 L/min, non-invasive positive pressure ventilation, mechanical ventilation, or ECMO, or clinical diagnosis of respiratory failure (exclusion criteria 1.c.i) at any time during the 28 days after randomization. Note that those who experience mortality after respiratory failure are still counted towards this analysis. Those who experience mortality without prior respiratory failure will not be counted towards this analysis.

8.2.4 Among patients that do not experience respiratory failure in the first 28 days, time to initiation and duration of supplemental oxygen or other respiratory support within the first 28 days

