The number of days of supplemental oxygen or other respiratory support in patients not meeting the criteria for respiratory failure from randomization through Day 28 will be summarized descriptively and analyzed using ANCOVA. The LS means will be presented along with the associated 95% CI within each treatment group. In comparing treatments, LS mean differences between treatments will be presented along with associated 95% CIs and p-values. For Part 1 analysis, this endpoint will be reported in all patients in the ITT population.

The time to start of supplemental oxygen or other respiratory support from randomization through Day 28 will be analyzed using a Cox-Proportional hazard model. The number of participants who experience the event and rate ratio with 95% CI will be presented. The p-value to test if the rate ratio between treatments differs from 1 will be evaluated. Kaplan-Meier methodology will be used to estimate the median time to the event and 95% CI. Censoring events include loss to follow-up prior to Day 28. Mortality will not be considered a censoring event and instead will be analyzed as if this patient was on supplemental oxygen or other respiratory support for all days between randomization and Day 28. If mortality or the event of interest does not occur, all subjects will be censored at Day 28. Covariates will include those a priori specified in [Section 6.1.2](#), and Efron's method for handling tied time-to-events will be used. The p-value testing for non-zero treatment effect will be obtained from a Wald chi-square test, and the 95% CI associated with the treatment effect will be a Wald-type CI.

Duration and time to supplemental oxygen or other respiratory support through Day 28 will be calculated according to [Section 6.1.7](#)

8.2.5. Among patients that experience respiratory failure in the first 28 days, time to initiation and duration of the forms of respiratory support meeting criteria outlined in critical COVID criteria (exclusion criteria 1.c.i) within the first 28 days

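### LOCF is the fallback for missing Day 28 primary outcomes and WHO scores, and no planned sensitivity analysis tests it

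*SAP*

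**What the plan says.** SAP 6.1.4, in line with Protocol 13.1 and 13.1.4, sets a two-step rule. First, "Missing data for reasons other than death will, when possible, be derived from contemporaneous clinical data". Second, where those data are lacking or do not settle the outcome, "data will be imputed based on the last available value (last observation carried forward"). Deaths are handled separately, by assigning the worst value.

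Other sections limit how far the second step reaches:

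- **Mortality (SAP 8.2.2 and 6.1.7):** "Censoring events include loss to follow-up prior to Day 60", with time ending at last follow-up.
- **Time to oxygen or respiratory support (SAP 8.2.4 and 8.2.5):** "Censoring events include loss to follow-up prior to Day 28".
- **Adverse events (SAP 9.1):** missing severity and missing relationship have their own imputation rules.

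No such exception is given for the primary endpoint (SAP 8.1) or the WHO scale (SAP 8.2.1). The WHO scale is analysed by ANCOVA at each scheduled post-baseline visit, and the endpoint runs to Day 60.

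SAP 8.1.1 plans two types of sensitivity analysis for the primary and key secondary endpoints: covariate selection and stratified estimates. Protocol 13.1 adds that "Primary and secondary efficacy endpoints will be tabulated according to the" Observed Cases approach, without saying which outputs use observed data and which use imputed data.

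**The concern.** LOCF assumes that a participant's status stays fixed after the last contact. In severe COVID-19 most participants either recover or deteriorate over the following weeks, so the assumption is doubtful in both directions.

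On the primary endpoint the rule is optimistic: any later respiratory failure or death in a lost participant goes uncounted. The derivation in SAP 6.1.7 points the same way, because survival there rests on there being no report of death. On the WHO scale the rule is pessimistic for people who leave while in hospital, since their later recovery is not seen. A participant who withdraws on Day 5 on low-flow oxygen (score 4) would be a success on the primary endpoint and also be analysed as hospitalised on oxygen at Day 60.

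If loss differs between arms, the treatment comparison is biased. Even if it does not, a single imputed value treated as data understates the uncertainty. As planned, no output would show a reader how much the result depends on the rule.

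**Working it through.** The plan states no power, effect size or dropout rate, so there is no figure of its own to reproduce. The allocation is consistent: 18 at 5:5:5:3 gives 5, 5, 5 and 3; 72 at 1:1 gives 36 and 36; the total is 90 (SAP 3.2).

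**Step 1. Weight of one reclassified participant.** The shift in an arm's proportion is 100/n points.

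- Part 2 arm: 100/36 = 2.8 points.
- Part 1 active arm: 100/5 = 20.0 points.
- Part 1 placebo arm: 100/3 = 33.3 points.

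This is the weight of one person, not yet a bias.

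**Step 2. Expected bias in one arm's success proportion.** Let d be the fraction lost and carried forward as successes, and q the true success rate among them. The upward bias is d × (1 − q). Both d and q are assumptions.

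| Loss d | q = 50% | q = 70% | q = 90% |
|---|---|---|---|
| 5% | 2.5 points | 1.5 | 0.5 |
| 10% | 5.0 | 3.0 | 1.0 |
| 20% | 10.0 | 6.0 | 2.0 |

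**Step 3. Bias in the risk difference.** This is the difference between the two arms' biases. If d and q are the same in both arms, it is zero. With an assumed 5% loss in one arm, 15% in the other and q = 70% in both, it is 0.15 × 0.30 − 0.05 × 0.30 = 0.045 − 0.015 = 0.030, or 3.0 points in favour of the arm that loses more people.

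**Step 4. WHO scale at Day 60.** If a fraction d leaves at score 4 and the true Day 60 score is t, the arm mean is raised by d × (4 − t). Taking t as 1 or 2 (assumed), so that 4 − t is 3 or 2:

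- 5% loss: 0.10 to 0.15 points.
- 10% loss: 0.20 to 0.30 points.
- 20% loss: 0.40 to 0.60 points.

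**Step 5. Check against the planned sensitivity analyses.** Varying the covariates or stratifying the estimate leaves the imputed outcomes unchanged. Neither type in SAP 8.1.1 can therefore show how far the result depends on LOCF.

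**The case against.** The strongest reply is that LOCF will seldom be needed. It comes second to contemporaneous clinical data. The WHO scale is scheduled daily to Day 21 and then on Days 28, 45 and 60, and post-discharge contacts may be by phone or ePRO outside the in-person visits (Protocol 2.2). Stopping study drug is not leaving the study (Protocol 9.5.1), and end-of-study evaluations are sought at withdrawal (Protocol 9.4). This stands, and it limits the likely size. It does not remove the point: Protocol 9.4 reserves withdrawal of consent for people who no longer allow their outcome data to be pursued, and for them the first step may yield nothing.

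The second reply is that the current report is not the analysis criticised. SAP section 10 records that recruitment was paused with one Part 2 participant, and that Part 1 (N=18) will be reported with summary statistics and confidence intervals but no efficacy P values. That also stands. The modelling points concern Part 2 and the Combined Population, in an exploratory trial without a power calculation.

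A reader might also infer four stronger things that the documents do not support:

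- **LOCF governs all non-death missing data.** It does not; the Cox analyses censor, and adverse events have their own rules.
- **Early withdrawals count as hospitalised to Day 60.** This holds for WHO scores only. Hospitalisation days end at Day 28.
- **Participants with a missing baseline sPLA2 or BMI drop out of the ITT model.** The SAP states no rule for this case, but sPLA2, height and weight are all collected at screening (Protocol 10.2.1). The sentence "Each of these variables will be assessed at baseline, prior to randomization" concerns timing only, and nothing suggests that such gaps will occur.
- **Observed Cases contradicts the imputation rule.** The protocol says endpoints are tabulated that way, which can be read as covering descriptive tables only. The text needs clarifying, but a contradiction is not shown.

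**Conclusion.** The point holds in a limited form. For the primary endpoint and the WHO scale, LOCF decides the outcome whenever clinical records cannot, its direction differs between the two endpoints, and no planned analysis tests it.

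The size is uncertain because no dropout rate is given. The 3-point bias in the risk difference rests on assumed unequal loss (5% versus 15%) and 70% true success among those lost; equal loss with equal true success gives none. The understatement of uncertainty was not quantified.

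A reader might infer that everyone lost after discharge becomes a success. That is certain only for those with no prior respiratory failure and no other data. For someone who had respiratory failure and recovered, it depends on whether the endpoint means status at Day 28 or any failure up to Day 28, which the SAP leaves open.

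This is an improvement that should be made before any Part 2 or Combined analysis. In the Part 1 report it matters only if a Day 28 status was actually imputed, but with 3 to 5 per arm one such participant would dominate the proportion.

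**What to change.** **Primary endpoint, Part 2 and Combined analyses.** Keep the contemporaneous-data step. Where it does not settle Day 28 status, replace LOCF with multiple imputation from treatment, the baseline covariates and the last WHO score. Add a tipping-point table over the number of imputed failures in each arm, and keep LOCF as a sensitivity analysis.

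**WHO scale.** Use the same multiple imputation before the by-visit ANCOVA. Alternatively, fit a repeated-measures model on a few prespecified visits with a structured covariance. In either case death stays at 8. Using every visit would be impractical: Days 2 to 21 plus Days 28, 45 and 60 make 23 visits, and an unstructured covariance would then need 23 × 24/2 = 276 parameters from 72 participants.

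**Observed Cases.** State that it applies to descriptive tables only.

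**Part 1 report.** Multiple imputation is not practical with 3 to 5 per arm. Show best-case and worst-case bounds for any participant whose Day 28 status is imputed.

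**Cost.** SAP wording, modest programming and some added analysis work. SAP section 10 already foresees a protocol and SAP amendment for Part 2, though for other endpoints, and these changes could go into it.
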